#### Exclusion Criteria

- Subjects must not have an existing diagnosis of a neurodegenerative disorder (e.g., Alzheimer's Disease, Lewy Body Dementia, Frontal-Temporal Dementia).
- Subjects must not have a prior diagnosis that might impact cognition and movement abilities including: significant cardiovascular disease, significant respiratory disease, illness or injury, substance abuse, schizophrenia, bipolar disorder, or other neurological diseases.
- Subjects must not have a previous Mini Mental State Exam (MMSE) score below 19.
- Subjects must not have a previous Clinical Dementia Rating (CDR) global score of  $\geq 2$ .
- Subjects must not have a Montreal Cognitive Assessment (MoCA) score of below 18 previously or during their screening evaluation.
- Subjects must not demonstrate a progression of aMCI to dementia at screening based on the best judgement of a study Clinical Neuropsychologist.
- Subjects must not currently participate in a high level of physical activity prior to study start as assessed by the International Physical Activity Questionnaire (IPAQ) at screening.
- Subjects must not endorse that they are unable to participate in moderate intensity aerobic activities, such as fast walking or passing/kicking a ball to a partner at screening.

Participants may enroll in the RCT but not receive a brain MRI if they do not pass MRI screening. Participants will be excluded from MRI procedures (but not the RCT) if they have any of the following:

- Brain Aneurysm Clip
- Implanted neural stimulator
- Implanted cardiac pacemaker or defibrillator
- Cochlear implant
- Ocular foreign body (e.g. metal shavings)
- Other implanted medical devices (e.g. Swan Ganz catheter)
- Insulin pump
- Metal shrapnel or bullets in their bodies
- They are pregnant (participants who are uncertain as to whether they are pregnant will be required to have a screening urine or blood pregnancy test)
- They have had surgery of uncertain type where the presence of metal clips or wires cannot be excluded.
- They have unstable angina or New York Heart Association functional class IV heart failure

Participants with claustrophobia may participate in a truncated MRI protocol under sedation, if they elect to participate.

### **Randomization**

A computerized randomized block design will be used for subjects who meet inclusion and exclusion criteria. Study staff will not see the assignments to arms provided by the computer in advance.

### **Data Collection and Assessments**

We will monitor participants in the RCT for up to 26 weeks and perform evaluations to determine cognitive trajectory between the two arms. . Total participation will be approximately 6 months. We will specifically evaluate data consisting of biomarkers (BDNF, NE), QEEG metrics (for example, peak alpha frequency), brain MRI, lifestyle, physical activity, and objective and subjective neurocognition. We will use statistical and computational methods in an effort to explain the causal underpinning of any observed differences between the two arms.

At **pre-screening**, the following will occur:

- Phone screening
- Medical records release to confirm eligibility and determine if they will require additional assessments at screening

At **Screening**, the following will occur:

- Informed consent
- Intake questionnaires
- MRI Safety Screening Questionnaire
- May be required to participate in a brief memory assessment
- PARQ+ and Medical Clearance to Exercise
- Virtual neuropsychological, cognitive, and functional assessments. If clinical neuropsychologist determines that the participant has progressed to dementia or the participant scores below 18 on the MOCA, participant will not pass screening

At **Baseline**, the following will occur:

- Randomization into Group 1 or Group 2
- Biomarker draw (blood)
- Physical status assessment including: physical measurements and questions regarding current physical status
- QEEG Assessment
- Brain MRI (unless contraindicated based on MRI Safety Screening Questionnaire)
- Participant receives Fitbit device and information on usage
- On-going collection of lifestyle data from FitBit device

- Phone call with study staff for patient to report one week's cognitive activity
- Group 2 (mSIM): Participant receives binder with homework to be completed during the course of the mSIM intervention
- Group 2 (mSIM): Participant signs credit card authorization form for damages to study equipment. Form will be shredded at the end of study when participant returns all study equipment
- Group 2 (mSIM): Stationary bike is adjusted for the participant, and they receive instruction on the proper use of the bike
- Group 2 (mSIM): Participant receives instruction on the tablet and mobile application usage
- Group 2 (mSIM): Participant may be required to see a cardiologist for medical management as part of their standard of care if additional ischemic or hypertensive risk factors are uncovered during the physical status assessment. If participant's blood pressure continues to be above ACSM guidelines and the participant cardiologist will not clear them to participate in a moderately intense, unsupervised exercise program, the participant will be withdrawn from the study 

**Study equipment set-up**, the following will occur:

- On-going collection of lifestyle data from FitBit device
- Group 2 (mSIM): Delivery company will set up study equipment at participant's home
- Group 2 (mSIM): 2 (but up to 6\*) weeks aerobic exercise ramp-up using the exercise equipment provided

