**Study equipment break-down (Group 2: mSIM):**

- Delivery company will breakdown and remove equipment from participant's home

**Post-trial testing**, the following will occur:

- Virtual neuropsychological, cognitive, and functional assessments.
- Biomarker draw (blood)
- Physical status assessment including: physical measurements and questions regarding current physical status
- QEEG Assessment
- On-going collection of lifestyle data from FitBit device
- Phone call with study staff for patient to report one week's cognitive activity
- Brain MRI (unless contraindicated based on MRI Safety Screening Questionnaire)
- Group 2 (mSIM): Participant satisfaction with mSIM program through a survey

If participant wants to receive compensation for participation, participant must provide a W9 to study staff before the end of study.

\*The optimal exercise ramp-up duration is 2 weeks based on our prior exercise study in this population. However, participants may require up to 6 weeks depending on their baseline physical activity levels and ability to tolerate the aerobic exercise ramp-up phase. If, after 6 weeks of ramp-up, participants are unable to sustain 40-60%HRR during their exercise sessions, they may then be withdrawn from the trial by the principal investigator.

See **APPENDIX I** for a table view of the study timeline. Note all timepoints might be plus or minus one week.

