#### **4. EVALUATIONS AND ASSESSMENTS**

##### Physical Status Assessment

Each participant who is randomized into the RCT will undergo a physical status assessment. During the physical status assessment participants will have their blood pressure, weight, and waist and hip circumferences measured. This assessment will occur at baseline and post-trial for Group 1 and Group 2 participants.

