## **6. ANALYTICAL METHODS**

To determine feasibility of the protocol, we will analyze adherence and feasibility data from participants via a secure data-aggregation program from which will pull de-identified FitBit session data and also from the session dashboard profiles from the mSIM web-based application. During the intervention, we will collect data related to program adherence in the mSIM web-based application.

In order to determine whether the mSIM treatment protocol produces significant improvements in cognitive abilities, our primary analytic tool will be the linear regression model, which will be implemented as an ANCOVA in SPSS or similarly capable statistical software (e.g., R statistical software and SAS). Outcomes will be the post-trial assessment measurements, baseline measurements of the outcomes will be used as covariates, and treatment group (Group 2 (mSIM) or Group 1 (CON)) will be the key variable to assess the treatment effect.

We will also perform an analysis of peripheral biomarker data to help us understand the biological underpinnings of any cognitive changes produced by the mSIM treatment protocol. Outcomes will be the post-trial biomarker measurements of BDNF or NE corrected concentration levels, baseline measurements of BDNF or NE corrected concentration levels will be used as covariates, and treatment group (Group 2 (mSIM) or Group 1 (CON)) will be the

key variable to assess the treatment effect. We will also conduct an exploratory analysis where we will evaluate the extent to which changes in BDNF and NE separately relate to changes in memory performance (composite memory Z-score) through correlational analyses.

To quantify the effects of the mSIM intervention on cognitive inhibitory tone, we will perform an analysis of the QEEG data. Our primary indicator is a metric called peak Alpha frequency. Outcomes will be the post-trial peak alpha frequency, baseline measurements peak alpha frequency will be used as covariates, and treatment group (Group 2 (mSIM) or Group 1 (CON)) will be the key variable to assess the treatment effect. We will also conduct an exploratory analysis where we will evaluate the extent to which changes in peak alpha frequency separately relate to changes in memory performance (composite memory Z-score) or other biomarker data through correlational analyses. Additional metrics from the QEEG will be explored. EEG will be provided in-kind by Evox and not the NIA-funded study.

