## **10. SUBJECT DISCONTINUATION AND TERMINATION OF STUDY**

Although subjects will be encouraged to complete the study, they may voluntarily withdraw at any time. The investigator will document the reasons for discontinuation.

Also the investigator may withdraw the subject from the study. The subject will be removed from the study without their consent for various health, safety or administrative reasons, including but not limited to the following:

- The investigator decides that continuing in the study would be harmful to subject.
- The sponsor cancels the study.
- Other administrative reasons.

The investigator will make the decision and let the subject know if it is not possible for him/her to participate.

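### Two rules that act after randomisation can remove mSIM participants, but not CON participants, from the study, and the plan sets out no later outcome testing and no as-randomised analysis

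*Combined protocol and SAP*

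**What the plan says.** All references are to the combined protocol and SAP.

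- **Order of events.** Section 3, Data Collection and Assessments, opens its Baseline list with "Randomization into Group 1 or Group 2". Appendix I gives randomisation its own column, ahead of Baseline.
- **Rule (a), mandatory.** A Baseline bullet labelled for Group 2 sets two conditions: "If participant's blood pressure continues to be above ACSM guidelines and the participant cardiologist will not clear them". The consequence is removal from the study, in the words "the participant cardiologist will not clear them to participate in a moderately intense, unsupervised exercise program, the participant will be withdrawn from the study". Blood pressure is part of the physical status assessment, which both arms have. Section 4 says: "This assessment will occur at baseline and post-trial for Group 1 and Group 2 participants". No Group 1 counterpart to the rule appears.
- **Rule (b), discretionary.** The ramp-up footnote at the end of the visit lists reads: "If, after 6 weeks of ramp-up, participants are unable to sustain 40-60%HRR during their exercise sessions, they may then be withdrawn from the trial". The principal investigator decides. Only Group 2 has a ramp-up.
- **After withdrawal.** Section 10 asks for little: "The investigator will document the reasons for discontinuation". It describes no further assessment.
- **Analysis.** Section 6 specifies ANCOVA: "Outcomes will be the post-trial assessment measurements, baseline measurements of the outcomes will be used as covariates". The biomarker model has the same form ("Outcomes will be the post-trial biomarker measurements of BDNF or NE corrected concentration levels"), as does the peak alpha model. Section 6 names no analysis population and no method for missing data.
- **Safeguards before allocation.** The inclusion criteria require physician clearance for moderate unsupervised exercise, and screening includes the PARQ+. Both apply to all candidates.

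**The concern.** Section 2 makes efficacy on memory and everyday functioning a major objective, and Section 3 hopes to explain causally any difference between arms. Both depend on the arms staying comparable after allocation.

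Rules (a) and (b) end study participation, not only training. A CON participant with the same blood pressure or the same exercise tolerance stays in and supplies a post-trial score. If a withdrawal under either rule occurs, the ANCOVA has no outcome for that person and compares a filtered mSIM group with an unfiltered CON group.

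Adjusting for the screening score does not repair this. The selection acts through whatever part of the post-trial score is related to blood pressure or tolerance but not predicted by the screening score. With 15 per arm, each removal is 1/15 = 6.7% of the arm.

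**Working it through.** The plan states no power, effect size, SD, significance level or withdrawal rate, so there is no figure of its own to reproduce.

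**Inputs from the documents.** 15 per arm; ANCOVA on the post-trial score; removal possible in mSIM only.

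**Assumptions.** No true effect; two-sided 5% test; residual SD 1; screening slope 0.7; k = 1 to 4 of 15 removed, exactly the least tolerant; correlation rho = 0.2 to 0.5 between tolerance and the baseline-adjusted post-trial score.

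**Bias formula.** Removing the k lowest of 15 on tolerance raises the mean tolerance of those left by S_k/(15 - k). S_k is the sum of the k largest expected normal order statistics for n = 15 (1.736, 1.248, 0.948, 0.715). Bias = rho x S_k/(15 - k).

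- k = 1, rho 0.2: 0.2 x 1.736/14 = 0.2 x 0.124 = 0.025 SD
- k = 2, rho 0.3: 0.3 x 2.984/13 = 0.069 SD
- k = 3, rho 0.3: 0.3 x 3.932/12 = 0.098 SD
- k = 4, rho 0.5: 0.5 x 4.647/11 = 0.211 SD

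**Simulation of the ANCOVA** (100,000 replicates per cell; smaller independent re-runs agreed within simulation error):

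| Removed | rho | Who is tested | Bias (SD) | Type I error |
|---|---|---|---|---|
| 1 | 0.2 | none of those removed | 0.024 | 5.1% |
| 2 | 0.3 | none | 0.069 | 5.4% |
| 3 | 0.3 | none | 0.097 | 5.8% |
| 4 | 0.5 | none | 0.212 | 8.2% |
| 4 | 0 | none | -0.001 | 5.0% |
| 4 | 0.5 | 2 of the 4 | 0.090 | 5.5% |
| 4 | 0.5 | all 4 | within 0.002 of 0 | about 5% |

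If removal follows tolerance only loosely (correlation 0.5), the bias is 0.012-0.106 SD and the error 5.0-5.8%. A negative rho reverses the sign: k = 4, rho -0.5 gives -0.21 SD.

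**Scale.** The detectable difference at 80% power (noncentral t, df = n1 + n2 - 3, noncentrality d/sqrt(1/n1 + 1/n2)) is 1.06 SD for 15 v 15 and 1.16 SD for 11 v 15. Lost precision is therefore minor. The bias is 0.025/1.06 = 2% to 0.21/1.06 = 20% of the detectable difference.

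**Can imputation replace testing?** Filling in the value predicted from screening leaves the bias where it was (0.212 v 0.212 at k = 4, rho 0.5). Subtracting a fixed shift can cancel the bias, at bias x 15/k, but treats invented scores as data:

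- k = 4, rho 0, no shift: error about 9.5%, against 5.0% complete-case.
- k = 4, rho 0.2, shift 0.32 SD (which cancels the bias): error about 9.3%, against about 5.4%.
- k = 4, rho -0.5, downward shift of 1.0 SD: bias goes from -0.21 to -0.48 SD.

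**The case against.** The best defence is that this will hardly ever bite. Section 1 calls the trial a pilot and Section 6 opens with feasibility. Physician clearance, the PARQ+ and the exclusions for significant cardiovascular and respiratory disease all come before allocation. Rule (a) needs two conditions together, and rule (b) says only that withdrawal may follow. With 2-3 removed the error rate barely moves. The 8% figure needs 27% of the arm removed, exactly the least tolerant, at rho 0.5. All of this stands and lowers the weight of the point. It does not remove the asymmetry, and efficacy remains a declared objective.

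Three stronger readings are tempting, and the documents do not support them:

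- A reader might infer that the rules bias the trial towards mSIM. That requires those removed to score worse than their screening score predicts, and nothing in the documents establishes it.
- A reader might add the COVID-19 termination rule in Section 11 as a third rule of this kind. It is worded for any participant and is not arm-specific.
- A reader might say that the trial makes no provision at all for withdrawn participants. Some pages were not in the text reviewed, so the claim is only that Sections 3, 6 and 10, where such provisions would belong, contain none.

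**Conclusion.** The structural point holds. One mandatory and one discretionary rule, both operating after allocation, can take mSIM participants out of the study with no CON counterpart, and nothing in the reviewed text keeps their outcomes or fixes an as-randomised comparison. It is worth correcting, at modest weight.

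The size is conditional throughout, because the documents give neither the number removed nor rho. A plausible middle case is 0.07-0.10 SD with about 5.3-5.8% type I error. One removal at rho 0.2 gives about 0.03 SD, and 0.21 SD with about 8% error is the extreme. There is no bias if nobody is removed, if rho is 0, or if all those removed are tested. Confidence is high on the asymmetry and low on its practical size.

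**What to change.** Leave every clinical criterion for stopping training, and the investigator's right to withdraw a participant in Section 10, as written.

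1. In the Group 2 blood-pressure bullet and the ramp-up footnote (Section 3), change only the consequence for study participation. The person stops, or does not start, training but, where willing, stays in for the virtual mid-intervention and post-trial cognitive and functional testing, timed from randomisation to match the usual schedule.
2. In Section 6, state that all randomised participants with a post-trial score are analysed in their assigned arm whether or not they trained, and that withdrawals are reported by arm and reason.
3. If post-trial scores are still missing in either arm, add a sensitivity analysis by multiple imputation, or another method that carries imputation variance. Apply shifts in both directions, for example -1.0 to +1.0 SD, separately by arm. Do not use single fixed-value imputation.
4. Offer post-trial blood, QEEG and MRI to those who stop training, or state that those comparisons remain exposed.

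**Cost.** A short amendment with ethics review and any consent revision. At the rates in Section 3, Compensation, the two virtual sessions cost 2 x $25 = $50 per person. Adding blood, QEEG and MRI brings this to 5 x $25 = $125, plus visit, scan and assay costs.

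**Downside.** The estimate becomes the effect of assignment to mSIM, diluted by 1/15 to 4/15 (about 7-27%) if 1-4 of 15 get no benefit. An as-trained analysis can be shown as supplementary. This version is dated October 2021, and Section 8 schedules monitoring-board meetings from before enrolment through 2021, so outcomes for anyone already withdrawn may not be recoverable.

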**Study intervention period:**

- Group 2 (mSIM): Begin 24-session mSIM exercise and cognitive training intervention (24x/12 weeks at home)
- Group 2 (mSIM): May be asked to take blood pressure before each exercise session if deemed necessary
- Group 2 (mSIM): Weekly calls with a member from the research staff for troubleshooting and navigating the mSIM program, and for checking homework completion

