## **2. OBJECTIVES OF THE STUDY**

One major study objective is to develop and conduct beta testing of a web-based application that will deliver a mobile-based simultaneous exercise and memory skills training program (mSIM) for aMCI patients. A second major objective of the study is to evaluate the efficacy of mSIM on memory performance and everyday functioning using two study arms: Group 1 or the activity monitoring control group (CON) and Group 2 or the activity monitoring plus

immediate treatment with the mSIM intervention group (mSIM). The CON will serve as the control group and be recommended to wear a Fitbit to track their physical activity habits, which has been shown to be an effective intervention to increase physical activity levels, throughout the duration of the intervention. They will also report one week's physical activity via phone calls with research staff at baseline, mid-intervention, and post-trial. Study objectives include measuring treatment related changes in quality of life and cognitive and functional abilities.

A third major objective of this study is to test mSIM treatment response on concentration levels of peripheral biomarkers [BDNF and NE] and neural markers (eg. peak alpha frequency) measured with QEEG. Study objectives include testing the relationship between increased peak alpha frequency, concentrations in BDNF and NE, and improvements in memory.

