**Mid-intervention testing:**

- Virtual neuropsychological, cognitive, and functional assessments
- Phone call with study staff for patient to report one week's cognitive activity
- Group 2 (mSIM): Participant satisfaction through a survey

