The ramp-up for mSIM participants will start with 2 days per week for 2-6 weeks, where they will be asked to maintain an aerobic intensity of up to 40-60% HRR for 10-40 minutes, depending on their baseline physical activity level. After the ramp-up phase the mSIM (Group 2) participants will begin the 12-week intervention, comprised of 2 times/week, 65-minute sessions. Each mSIM session will include up to 15 minutes of sedentary new memory skills introduction learning or review. They will then have a 5-minute warm-up on the bike (30% HRR), followed by 35 minutes of memory skills training and practice while aerobic cycling in their estimated 40-60% aerobic training zone. They will then have 5 min of interval training which is continuously monitored on the FitBit wrist-worn watch. The resistance level will be pre-set on their bike to meet their aerobic training zone. They will then finish with a 5-minute cool-down that may include a 5-minute summary of skills learned in the session. Participants will be instructed in the importance of staying within their target heart rate zone and not exceeding their heart rate zone. A research staff member will be available during the first 2 weeks of mSIM training sessions via phone to help with any technical issues the participant has during the training session. Participants will be asked to open the FitBit App during their training session to sync their FitBit and indicate the start and stop time of their training session on a session log, so data can be monitored in real-time with the Fitbit data aggregator by research staff and to aggregate study compliance data. All FitBit data will use a de-identified study email address so that no personal identifying data will be linked with either FitBit or the FitBit data aggregator. Participant will be trained on how to ensure they are within their individualized 40-60% HRR and of the safety reasons for not going above 60%HRR.

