### **Compensation**

Group 1 (activity monitoring group) will receive access to the web-based program after they complete their post-trial testing. All participants will be compensated per completed assessment (\$25.00 x ≤ 3 for neuropsychology testing, \$25.00 x ≤ 2 for QEEG assessment, \$25.00 x ≤ 2 for MRI assessment, \$25.00 x ≤ 2 for blood draw) not done during clinic visits to cover time, travel, and inconvenience. The mSIM participants will be compensated \$10 x ≤ 12 weeks for completing study-related activities, which will be paid out at the end of their study

participation if they have reached at least 80% compliance (19/24 sessions). This includes for the mSIM group: completing mSIM training sessions and homework. The activity monitoring group participants will be compensated the same total amount over the course of the study (\$10 x ≤ 12 weeks) for completing their study-related activities during the intervention, which will be paid out at the end of their study participation if they have reached at least 80% compliance (10/12 weeks). This includes daily wearing of the FitBit for an entire week and weekly syncing of the device, as well as completing cognitive activity monitoring. Parking validation will be provided for study-specific visits. If the participant is enrolled in the RCT and completes all study visits, intervention sessions, data collections, and completed their lab visits and QEEG not during clinic visits, the maximum amount they will receive is \$345. All participants will be able to keep their FitBit after they complete the intervention period.

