#### **Definition of an AE**

The following definition of an adverse event (AE) will be used for this study:

- Any untoward medical occurrence in an enrolled subject who underwent procedures required by the study.

An AE can be any unfavorable and unintended sign, symptom, or disease (new or exacerbated) occurring after starting the procedures required by the study, even if the event is considered not related to the study procedures.

As far as possible, each adverse event will also be described by its duration (start and end dates), the intensity, its expectedness related to the known risks associated with the study procedures, and the action(s) taken.

It is the responsibility of the investigator to perform periodic and special assessments for AEs. The investigator and clinical staff will note all AEs reported by the subjects. All clinical complaints volunteered by, or elicited from, the subject during the study will be recorded separately on the appropriate page of the CRF. If any AE occurs, the subject will receive appropriate treatment and medical supervision if warranted.

All AEs judged to be clinically significant will be followed until resolution.

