### **APPENDIX I. STUDY TIMELINE (IN MONTHS) THE MSIM TRIAL RCT**

Each participant (N=30) will be enrolled for up to 26 weeks (6 months). Participants in the active arm (N=15, Group 2) arm will have the “mSIM Intervention” sessions outlined below, and patients in the control arm will only have activity monitoring via FitBit device. Group 1 will be granted access to the mSIM web-application after completing the intervention.

	Screen	Randmz.	Baseline	1 Mo	2 Mo	3 Mo	4 Mo	5 Mo	6 Mo	Post-Trial
Visit Window	-30 to -1 days	+/- 7 days	+/- 7 days	+/- 7 days	+/- 7 days	+/- 7 days	+/- 7 days	+/- 7 days	+/- 7 days	
*Consent & screening	1x									
*Intake questionnaires and assessments	1x									
Medical Clearance to Exercise	1x									
Randomization		1x								
Credit card authorization			1x							
Physical status assessment			1x						1x	
Lifestyle and/or satisfaction data			1x				1x	1x		
mSIM Intervention (Group 2 (SIM))										
Equipment instruction			1x							
Equipment drop-off			1x							
Equipment pick-up								1x		
Exercise ramp-up session				4-12x (2-6 weeks duration)						
Gain access to mSIM web-app						✓				
Virtual Support Sessions						✓				
mSIM exercise session				24 x (12-14 weeks duration)						
mSIM homework				24x (12-14 weeks duration)						
mSIM Intervention (Group 1 (CON))										
Access to mSIM web-app										1x
On-going Data Collection										
Fitbit					✓					
Imaging Data Collection										
QEEG			1x					1x		
MRI*			*1x					*1x		
Biological Sample Collection										
Blood sample			1x					1x		
Neuropsychological/Cognitive Assessments										
Virtual neuropsychological assessment	1x						1x	1x		

Notes: #x indicates the number of times a test or an intervention will occur in protocol window (e.g. 2x = two times). \*In participants that are eligible for an MRI.

✓ indicates ongoing data collection.

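### AE enquiry is tied to no scheduled contact, and the staff contact that is scheduled is unequal between arms and not listed during exercise ramp-up

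*Combined protocol and SAP*

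**What the plan says.** On AE collection, section 8 (Definition of an AE) gives the investigator a duty of periodic and special AE assessment in enrolled subjects, and adds: "All clinical complaints volunteered by, or elicited from, the subject during the study will be recorded separately on the appropriate page of the CRF". It states no interval, no wording and no visit. Section 8 also requires a monthly report of all AEs to the DSMB Chair.

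On contact in the mSIM arm, the Study intervention period list in section 3 has, for Group 2 only, "Weekly calls with a member from the research staff for troubleshooting and navigating the mSIM program, and for checking homework completion". Ramp-up stands in the preceding Study equipment set-up list, as "2 (but up to 6\*) weeks aerobic exercise ramp-up using the exercise equipment provided", and no call is listed there. The description of the mSIM programme in section 3 adds phone availability for technical problems, but only for the first two weeks of the mSIM training sessions, which follow ramp-up.

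On contact in the control arm, section 2 says: "They will also report one week's physical activity via phone calls with research staff at baseline, mid-intervention, and post-trial". The Mid-intervention testing list, which applies to both arms, has "Phone call with study staff for patient to report one week's cognitive activity". The two sections differ on what the calls are about but agree on when they happen. Between those points Appendix I says that "patients in the control arm will only have activity monitoring via FitBit device", and the control arm's weekly task under Compensation is a device task: "This includes daily wearing of the FitBit for an entire week and weekly syncing of the device".

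**The concern.** If AEs are recorded when a participant mentions them or is asked, the number recorded depends partly on how often someone speaks to the participant. A plan that schedules weekly conversations in one arm and a few in the other can produce a difference in AE counts that has nothing to do with the intervention.

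The ramp-up gap is a second and separate matter. Ramp-up is the first study exercise, done at home without supervision by people whom the exclusion criteria require not to be highly active at entry. The protocol itself foresees that some will tolerate it poorly, since its length depends on tolerance. Yet this is the one exercise period with no listed staff call.

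What is at stake is safety reporting. The DSMB subsection of section 8 describes the trial as low risk, and this pilot is where that description would be checked. An excess of AEs in mSIM could be an artefact of contact, and a quiet ramp-up could mean that nobody asked.

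**Working it through.** The check is a count of scheduled contacts. No power or alpha figure is involved.

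**1. Reproduce the plan's own session counts.** Section 3 says: "The ramp-up for mSIM participants will start with 2 days per week for 2-6 weeks".
- Ramp-up: 2 per week × 2 weeks = 4, and 2 per week × 6 weeks = 12. This matches the 4 to 12 sessions in Appendix I.
- Intervention: 2 per week × 12 weeks = 24. This matches the 24 sessions in section 3 and Appendix I.

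**2. Count listed phone contacts per participant.**

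| Period | mSIM | Control |
|---|---|---|
| Baseline | 1 | 1 |
| Ramp-up (2 to 6 weeks) | 0 | 0 |
| Intervention, weekly | about 12 | 0 |
| Mid-intervention | 1 | 1 |
| Post-trial | 1 | 1 |
| Total after baseline | 12 + 2 = 14 | 2 |

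This takes one weekly call per intervention week and assumes that none is merged with the mid or post call. Appendix I allows the 24 sessions to take 12 to 14 weeks, so the weekly count could be slightly higher. The table counts phone calls only. Both arms also have virtual assessments at mid-intervention and post-trial, and a physical status assessment at baseline and post-trial. These add equally to both arms, so the difference of about 12 contacts stays, although the 14-to-2 ratio would shrink.

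**3. Length of the gaps.** Assume that mid-intervention falls at week 6 of 12 and that the control calendar follows the mSIM one.
- Baseline to mid: 2 + 6 = 8 weeks, to 6 + 6 = 12 weeks.
- Mid to post: 12 − 6 = 6 weeks.

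A control participant would then go 8 to 12 weeks, and later about 6 weeks, without a listed conversation. An mSIM participant goes 2 to 6 weeks in ramp-up without one, and is then called weekly.

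**4. Share of exercise in the period without calls.**
- Shortest ramp-up: 4 / (4 + 24) = 4/28 = 14% of sessions.
- Longest ramp-up: 12 / (12 + 24) = 12/36 = 33%.
- Across 15 mSIM participants: 15 × 4 = 60 to 15 × 12 = 180 sessions.

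**5. Look for an AE question.** None of the section 3 visit lists and no row of Appendix I names an AE enquiry. The stated purposes of the weekly calls are technical help and homework. The nearest item is the physical status assessment, which includes questions on current physical state in both arms at baseline and post-trial, but is not described as AE collection.

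**6. Direction.** If complaints come up in conversation, the arm with more conversations will tend to have more recorded, which is mSIM during the intervention. In ramp-up the likely error is the opposite one, mSIM events missed or reported late. The documents give no AE rate and no capture rate, so neither effect can be sized.

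**The case against.** The strongest reply is that the duty in section 8 applies to every enrolled subject in both arms, whatever the call schedule. Section 8 also describes clinical monitoring as continuous and requires monthly AE reports, and section 7 includes monitoring for safety. If the investigator assessed both arms equally and often, the imbalance in calls would matter little. This stands, and it rules out saying that AEs are in fact under-collected in control or in ramp-up, which a reader might infer from the contact counts. What the reply does not supply is a schedule. A monthly report to the DSMB Chair fixes when AEs are passed on, not when participants are asked.

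Second, absence of a listed call in ramp-up is not proof of no contact. Extending ramp-up by tolerance, or withdrawing someone who cannot hold the target zone after six weeks, implies that staff follow participants in some way. Appendix I also has a row for virtual support sessions, whose column position cannot be read reliably from the extracted text. Both points stand. They make some contact likely, but neither makes it scheduled or an AE enquiry.

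Third, the weekly calls are not symptom calls, so one cannot also assume that they capture most AEs. This stands too. A false between-arm ratio could be produced only by assuming capture rates, and would merely restate them.

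Fourth, section 6 plans no between-arm AE analysis, and 15 per arm would give little precision for one. Correct, so the consequence is confined to safety description and DSMB review.

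**Conclusion.** The point holds as a modest improvement to safety data collection. AE assessment is required but tied to no scheduled contact. Scheduled contact favours mSIM by about 12 calls per participant during the intervention, and none is listed for the 4 to 12 ramp-up sessions. Followed as written, the schedule may give arm-dependent ascertainment, probably with relatively more AEs recorded in mSIM during the intervention, and early exercise events may be missed or reach the DSMB late.

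This rests on the listed contacts being the main regular ones, and on unscheduled assessments not being equal and frequent enough to compensate. The documents neither confirm nor exclude the second.

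Three stronger readings should not be drawn. The documents do not show that AEs are under-collected. They do not support the view that complaints peak in ramp-up, for which they give no figure. And nothing here touches the ANCOVA of cognitive outcomes in section 6, which does not use AE data.

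**What to change.** (a) Add one short AE question set, worded identically for both arms, to the baseline, mid-intervention and post-trial contacts that both arms already have, and give it a row in Appendix I. At mid and post it should cover the whole interval since the previous common contact, including events already mentioned in a weekly call, so that the recall window is the same. Base any by-arm AE summary on these common time points. List AEs first reported in mSIM-only calls separately, split into ramp-up and intervention.

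(b) Start the existing weekly mSIM calls at the first ramp-up session, and put the same AE questions in the call script.

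Cost: wording in call scripts, one Appendix I row, and 2 to 6 extra short calls per mSIM participant, which is 15 × 2 = 30 to 15 × 6 = 90 calls in all. These come on top of the 15 × 12 = 180 weekly calls already planned. More minor AEs will be recorded.

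Part (b) also raises mSIM-only contact from about 12 calls to 14 to 18 per participant (12 + 2 to 12 + 6). That is why the by-arm summary must use the common time points. A residual limit is that weekly questioning may sharpen recall in mSIM at the common points, and the report should say so. No exercise prescription or clinical rule changes.
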